### 10.3.5. Reporting of SAEs

#### SAE Reporting via Electronic Data Collection Tool

- The primary mechanism for reporting SAEs will be the electronic data collection (EDC) tool.
- If the electronic system is unavailable, then the site will use the paper SAE data collection tool to report the event within 24 hours. Details to be provided in the Study Specific SAE Reporting Guidelines.
- The site will enter the SAE data into the electronic system as soon as it becomes available.
- The investigator or medically-qualified sub-investigator must show evidence within the eCRF (e.g., check review box, signature, etc.) of review and verification of the relationship of each SAE to IP/study participation (causality) within 24 hours of SAE entry into the eCRF.
- After the study is completed at a given site, the electronic data collection tool will be taken off-line to prevent the entry of new data or changes to existing data.
- If a site receives a report of a new SAE from a study participant or receives updated data on a previously reported SAE after the electronic data collection tool has been taken off-line, then the site can report this information on a paper SAE form (see next section) or to the SAE coordinator by telephone.
- Contacts for SAE reporting will be included in the Study Specific SAE Reporting Guidelines

### 10.3.6. Expedited Reporting to Health Authorities, Investigators and Ethics Committees

#### Expedited Reporting

The Sponsor or their third-party delegates will promptly evaluate all serious adverse events and non-serious adverse events to identify and expeditiously communicate new safety findings to investigators, IRBs, ECs, and health authorities based on applicable legislation as per the Expedited and Periodic Safety Reporting Plan.

To determine reporting requirements for single adverse event cases, the Sponsor or their third-party delegate will assess the expectedness of these events using the sotrovimab Investigator's Brochure.

## 10.4. Appendix 4: Contraceptive and Barrier Guidance

### 10.4.1. Definitions

#### 10.4.1.1. Woman of Nonchildbearing Potential (WONCBP)

Women in the following categories are considered WONCBP:

1. Premenopausal female with permanent infertility due to one of the following (for the purpose of this study):
  - a. Documented hysterectomy
  - b. Documented bilateral salpingectomy
  - c. Documented bilateral oophorectomy

For individuals with permanent infertility due to an alternate medical cause other than the above, (eg, Mullerian agenesis, androgen insensitivity, gonadal dysgenesis), investigator discretion should be applied to determining study entry.

**Note:** Documentation can come from the site personnel's review of the participant's medical records, medical examination, or medical history interview.

2. Postmenopausal female

A postmenopausal state is defined as no menses for 12 months without an alternative medical cause.

- A high FSH level in the postmenopausal range may be used to confirm a postmenopausal state in women not using hormonal contraception or hormonal replacement therapy (HRT). However, in the absence of 12 months of amenorrhea, confirmation with more than one FSH measurement (> 40 IU/L or mIU/mL) is required.
- Females on HRT and whose menopausal status is in doubt and in whom highly effective methods are contraception are required will be required to use one of the non-estrogen hormonal highly effective contraception methods if they wish to continue their HRT during the study. Otherwise, they must discontinue HRT to allow confirmation of postmenopausal status before study enrollment.

#### 10.4.1.2. Woman of Childbearing Potential (WOCBP)

Women in the following categories are considered WOCBP (fertile):

3. Following menarche
4. From the time of menarche until becoming postmenopausal or premenopausal with permanent infertility (see above)

**Note:** Documentation can come from the site personnel's review of the participant's medical records, medical examination, or medical history interview.

If fertility is unclear (eg, amenorrhea in adolescents or athletes) and a menstrual cycle cannot be confirmed before first dose of study intervention, additional evaluation should be considered.

VIR-7831  
Vir Biotechnology, Inc.

VIR-7831-5008 (GSK Study 217114)  
Amendment 4

#### 10.4.2. Contraception Guidance

Contraceptivesa Allowed During the Study Include:	
Highly Effective Methods b That Have Low User Dependency Failure rate of <1% per year when used consistently and correctly	

 
● Implantable progestogen-only hormone contraception associated with inhibition of ovulationb
 
● Intrauterine device (IUD)
 
● Intrauterine hormone-releasing system (IUS)b
 
● Bilateral tubal occlusion, bilateral tubal ligation, or bilateral salpingectomy
 
● Azoospermic partner (vasectomized or due to a medical cause)           
Azoospermia is a highly effective contraceptive method provided that the partner is the sole sexual partner of the woman of childbearing potential and the absence of sperm has been confirmed. If not, an additional highly effective method of contraception should be used. Spermatogenesis cycle is approximately 90 days.
 
Note: documentation of azoospermia for a male participant can come from the site personnel's review of the participant's medical records, medical examination, or medical history interview)

 
	
Highly Effective Methods b That Are User Dependent Failure rate of <1% per year when used consistently and correctly	

 
● Combined (estrogen- and progestogen-containing) hormonal contraception associated with inhibition of ovulationc 
 
– oral
 
– intravaginal
 
– transdermal
 
– injectable
 
 
 
● Progestogen-only hormone contraception associated with inhibition of ovulationc 
 
– oral
 
– injectable
 
 
 
	
Sexual abstinence	

Sexual abstinence is considered a highly effective method only if defined as refraining from heterosexual intercourse during the entire period of risk associated with the study intervention. The reliability of sexual abstinence needs to be evaluated in relation to the duration of the study and the preferred and usual lifestyle of the participant.
	
Effective Methods d That Are Not Considered Highly Effective Failure rate of ≥ 1% per year when used consistently and correctly	

 
● Progestogen-only oral hormonal contraception where inhibition of ovulation is not the primary mode of action
 
● Male or female condom with or without spermicidee
 
● Cervical cap, diaphragm, or sponge with spermicide
 
	

VIR-7831  
Vir Biotechnology, Inc.

VIR-7831-5008 (GSK Study 217114)  
Amendment 4

**Contraceptivesa Allowed During the Study Include:**

- A combination of male condom with either cervical cap, diaphragm, or sponge with spermicide (double-barrier methods)c

a Contraceptive use by men or women should be consistent with local regulations regarding the use of contraceptive methods for those participating in clinical studies.

b Failure rate of <1% per year when used consistently and correctly. Typical use failure rates differ from those when used consistently and correctly.

c Male condoms must be used in addition to hormonal contraception. If locally required, in accordance with Clinical Trial Facilitation Group (CTFG) guidelines, acceptable contraceptive methods are limited to those which inhibit ovulation as the primary mode of action.

d Considered effective, but not highly effective - failure rate of  $\geq 1\%$  per year. Periodic abstinence (calendar, sympto-thermal, post-ovulation methods), withdrawal (coitus interruptus), spermicides only, and lactational amenorrhea method (LAM) are not acceptable methods of contraception.

e Male condom and female condom should not be used together (due to risk of failure from friction).

Approved

VIR-7831  
Vir Biotechnology, Inc.

VIR-7831-5008 (GSK Study 217114)  
Amendment 4

2.0 (25-Oct-2021)	Amendment 3 (04-Oct-2021)	
 • Definition of ITT analysis set changed to match that in the protocol • Update to hypothetical estimand to detail key inclusion/exclusion criteria that lead to exclusion from population • Details of planned and ad hoc interim analyses added • Removal of 250mg IM dose from analyses and testing hierarchy • Region and vaccination status removed as covariates from analysis models, and the 12-17 years and 18-64 years age groupings combined in the age group covariate. • Methods for imputing COVID-19 progression status and viral load data corrected and clarified • Details added for cut-point used to define persistently high viral load • Inclusion of long COVID exploratory endpoint • Amend Week 24 timepoint to Week 36 due to increased length of follow-up in the study 	
Clarifications made to language in SAP to better align to language used in protocol amendments.
 
250mg IM arm removed from analyses and testing hierarchy due to being permanently discontinued from study at ad hoc interim analysis.
 
Model covariates amended due to small numbers of patients in non-US regions, small proportion of fully/partially vaccinated participants, and small number of participants <18 years.

SAP Version (Approval Date)	Protocol Version (Date) on which SAP is Based	Change	Rationale
		
• Addition of Kaplan-Meier plot summarizing time to undetectable viral load• Addition of new subgroup and PK-PD analyses.	

1. INTRODUCTION

The purpose of this SAP is to describe the planned analyses to be included in the Clinical Study Report for Study VIR-7831-5008. Details of the final Day 29 efficacy and safety analyses and 36-Week Safety Follow-Up analyses are provided.

Additional detail with regards to data handling conventions and the specification of data displays will be provided in the Output and Programming Specification (OPS) document.

1.1. Objectives, Estimands and Endpoints

Objectives	Endpoints
Primary	

 Evaluate the efficacy of two dose levels of intramuscular sotrovimab versus intravenous sotrovimab in preventing the progression of mild/moderate COVID-19 	
Progression of COVID-19 through Day 29 as defined by:
 
 Hospitalization > 24 hours for acute management of illness due to any cause OR Death
Secondary	
Safety 
 Describe the safety and tolerability of intramuscular and intravenous sotrovimab 	
 Occurrence of adverse events (AEs) Occurrence of serious adverse events (SAEs) Occurrence of adverse events of special interest (AESI) Occurrence of disease-related events

 Assess the immunogenicity of sotrovimab 	
 Incidence and titers (if applicable) of serum anti-drug antibody (ADA) to sotrovimab
Efficacy 
 Evaluate the efficacy of two dose levels of intramuscular versus intravenous sotrovimab on the progression of mild/moderate COVID-19 	
Progression of COVID-19 through Day 29 as defined by:
 
 Visit to a hospital emergency room for management of illness OR Hospitalization for acute management of illness for any duration and for any cause OR Death

Objectives	Endpoints

 Evaluate the efficacy of two dose levels of intramuscular versus intravenous sotrovimab in preventing COVID-19 respiratory disease progression 	
 Development of severe and/or critical respiratory COVID-19 as manifested by requirement for respiratory support (including oxygen) at Day 8, Day 15, Day 22, and Day 29

 Compare the virologic activity of sotrovimab given IM (two dose levels) or IV in reducing SARS-CoV-2 viral load 	
 Mean area under the curve of SARS-CoV-2 viral load in nasal secretions as measured by qRT-PCR from Day 1 to Day 8 (AUC_{D1-8}) Change from baseline in viral load by qRT-PCR at Day 8 Proportion of participants with a persistently high SARS-CoV-2 viral load at Day 8 by qRT-PCR
Pharmacokinetics 
 Assess the pharmacokinetics (PK) of sotrovimab in serum following IV and IM (two dose levels) administration 	
 IV and IM sotrovimab pharmacokinetics (PK) in serum
Exploratory	

 Describe the effect of two doses levels of intramuscular versus intravenous sotrovimab on incidence and duration of time on total hospital length of stay (LOS), incidence and duration of time on a ventilator, and ICU length of stay 	
 Incidence of hospitalization through Day 29 Total hospital LOS Proportion of participants requiring ICU stay or mechanical ventilation through Day 29 Total ICU LOS

 Monitor SARS-CoV-2 resistant mutants against sotrovimab 	
 SARS-CoV-2 resistance mutants to sotrovimab at baseline Emergence of viral resistance mutants to mAb by SARS-CoV-2

 Compare the virologic activity of sotrovimab given IM (two dose levels) or IV in reducing SARS-CoV-2 viral load 	
 Change from baseline in viral load in nasal secretions by qRT-PCR during follow-up period at Day 5, Day 11, Day 15, Day 22 and Day 29

Objectives	Endpoints
	
 Undetectable SARS-CoV-2 in nasal secretions by qRT-PCR at Day 3, Day 5, Day 8, Day 11, Day 15, Day 22 and Day 29 Mean area under the curve of SARS-CoV-2 viral load as measured by qRT-PCR from Day 1 to Day 5 (AUC_{D1-5}) and Day 1 to 11 (AUC_{D1-11})

 Compare the effect of different sample collection methods in SARS-CoV-2 viral load (e.g. nasopharyngeal swab, saliva) 	
 SARS-CoV-2 viral load measured by qRT-PCR

 Evaluate the effect of sotrovimab on the development of SARS-CoV-2 antibodies 	
 SARS-CoV-2 anti-N antibody at Day 1 and Day 29

 Describe the effect of sotrovimab on Long COVID symptoms 	
 Incidence and severity of Long COVID symptoms at Week 12, Week 24 and Week 36

Primary estimand

The primary efficacy endpoint will primarily be assessed using an estimand that uses a hypothetical strategy to deal with the main intercurrent events. The estimand is described by the following attributes:

- Population: All participants in the Intent-to-Treat (ITT) analysis set excluding participants who did not meet key inclusion/exclusion criteria (see section 4.2.2.1).
- Endpoint: Progression of COVID-19 through Day 29 as defined by hospitalization > 24 hours for acute management of illness due to any cause or death
- Summary measure: Absolute difference in the proportion of participants meeting the primary endpoint
- The anticipated intercurrent events are:
 - Not receiving randomized treatment or an alternative study treatment (i.e. treatment misallocation)
 - Discontinuation of study intervention as described in Protocol Section 7.1.
 - Use of medication not permitted during the study as listed in Protocol Section 6.8.1 up to Day 29

All intercurrent events will be handled using a hypothetical strategy where data collected after the occurrence of an intercurrent event will be excluded from the analysis, i.e. assuming the intercurrent event had not occurred.

Rationale for estimand: A hypothetical estimand is used as this is considered more conservative than treatment policy and therefore more appropriate for a non-inferiority comparison.

Supplementary Estimand for the Primary Endpoint

A supplementary estimand will be conducted based on all participants in the ITT analysis set by handling all intercurrent events with a treatment policy strategy (i.e. regardless of the intercurrent events occurring), with all the other attributes being the same as in the primary estimand. To estimate this estimand, all data collected in the ITT analysis set up to Day 29 will be included in the analysis.

[figure not shown]
[figure not shown]
Estimands for Key Secondary Endpoints

The estimand for the secondary endpoint 'Mean area under the curve of SARS-CoV-2 viral load in nasal secretions as measured by qRT-PCR from Day 1 to Day 8 (AUC_{D1-8})' is described by the following attributes:

- Population: All participants in the Virology analysis set, as defined in Section 3
- Summary measure: Treatment ratio (IM/IV) of mean \log_{10} AUC_{D1-8}
- Intercurrent events: Death and use of medication not permitted during the study as listed in Protocol Section 6.8.1 up to day 8
 - Strategy for Death: Composite strategy, where for participants who die prior to Day 8, the AUC_{D1-8} viral load value will be imputed using the worst AUC_{D1-8} viral load value from other participants in the same treatment arm.
 - The strategy for all the other intercurrent events (as applicable for this endpoint) will be treatment policy where data will be reported as captured.

The secondary endpoint 'Progression of COVID-19 through Day 29 as defined by visit to a hospital emergency room for management of illness OR Hospitalization for acute management of illness for any duration and for any cause OR Death' will be assessed using a hypothetical estimand as described for the primary endpoint. A supplementary treatment policy estimand will also be assessed using the same approach as the treatment policy estimand for the primary endpoint.

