4.2.2. Main analytical approach

The primary analysis will be conducted on the ITT analysis set, excluding participants who did not meet key inclusion/exclusion criteria (see section 4.2.2.1). All intercurrent events (see below) will be handled using a hypothetical strategy for the primary estimand, i.e. assuming the intercurrent event had not occurred.

The primary endpoint will be summarized using counts and percentages of the number of participants who have progression of COVID-19. The proportion of participants meeting the primary endpoint will be compared for sotrovimab 500 mg IM vs sotrovimab 500 mg IV using a 3.5% non-inferiority margin on the risk difference scale as per section 2.

The proportion of participants meeting the primary endpoint will be compared between treatments using a generalized linear model (GLM) from the binomial family with identity link, adjusted for treatment group (sotrovimab 500mg IV, sotrovimab 500mg IM), derived age group (<65 years old, ≥65 years old, see Section 6.2.7), and gender (female, male).

The absolute risk difference and associated 95% CI will be computed to test for non-inferiority in hypothesis (1).

Covariates may be removed from the model if it fails to converge as described in section 4.1.1. If the model still does not converge a GLM assuming a normal distribution for the endpoint and with identity link will be used, adjusted for the covariates above. If no events are observed on either treatment arm, the Farrington-Manning test will be used to compare arms.

The anticipated intercurrent events are:

- Not receiving randomized treatment or an alternative study treatment (i.e. treatment misallocation)
- Discontinuation of study intervention as described in Protocol Section 7.1.
- Use of medication not permitted during the study as listed in Protocol Section 6.8.1 up to day 29

Events are only deemed to be intercurrent events if they occur before occurrence of the primary endpoint. Data observed in the period following an intercurrent event (i.e. from the study day following the intercurrent event) will be excluded from the analysis. Data from this period will be assumed “missing at random” (MAR).

For participants that withdraw from the study and do not meet the primary endpoint at the time of withdrawal, data in the post-withdrawal period will also be assumed MAR.

Details of the method for multiple imputation is described in section 6.2.8.

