5. SAMPLE SIZE DETERMINATION

Sotrovimab IM participants and sotrovimab IV participants were planned to be enrolled and randomized in a 1:1:1 ratio to receive a single dose IV infusion of sotrovimab or a single IM injection of sotrovimab at one of two dose levels, in an open-label manner.

Approximately 1020 (340 per arm) participants were planned to be randomly assigned to study intervention. This sample size will provide approximately 90% power to demonstrate that IM

injection of sotrovimab is non-inferior to IV infusion of sotrovimab in terms of the proportion of participants with progression of COVID-19 through Day 29 at the one-sided 2.5% significance level assuming COVID-19 progression rates of 2% in the sotrovimab IM and IV arms and 3.5% non-inferiority margin on the risk difference scale.

Following the discontinuation of sotrovimab 250 mg IM arm (See Section 4.7), no more participants were enrolled and randomized into this arm. The remaining participants were randomized in a 1:1 ratio to receive sotrovimab 500mg IV or sotrovimab 500 mg IM

Sample Size/Power Sensitivity

The table below shows power for showing non-inferiority for different true progression rates on the sotrovimab IV arm and when the progression rate in the sotrovimab 500mg IM arm is equal to or higher than that on IV, given a sample size of N=340 per arm.

		Progression rate in sotrovimab IV arm		
		1.0%	1.5%	2.0%
Progression rate in sotrovimab IM arm minus Progression rate in sotrovimab IV arm	0% (equal)	>99%	96%	90%
	+0.1%	99%	95%	88%
	+0.2%	98%	93%	85%
	+0.3%	97%	91%	82%

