6.2.8. Statistical Modelling - Multiple Imputation

Multiple imputation will be used to impute data that is missing following withdrawal of the subject from the study, or following an intercurrent event for hypothetical estimands (if applicable), for the following two binary endpoints:

- Progression of COVID-19 through Day 29 as defined by hospitalization > 24 hours for acute management of illness due to any cause or death

- Progression of COVID-19 through Day 29 as defined by visit to a hospital emergency room for management of illness or hospitalization for acute management of illness for any duration and for any cause or death

Multiple imputation of endpoint data will be performed to impute data post study withdrawal or intercurrent event, as follows:

- Data will have a monotone missing structure so there will be no intermittent missing data.
- Imputation of missing data will proceed iteratively for each study day starting with Day 2 and ending at Day 29 using a logistic regression imputation model including the analysis model covariates and a parameter for COVID-19 progression status for the previous study day, i.e. imputation of COVID-19 progression status at Day X will include a covariate for status at Day X-1 from the previous imputation step.
- The “likelihood=augment” option in PROC MI will be used in the imputation to avoid quasi complete separation of data for the preceding timepoint covariate included in the imputation model. If logistic regression step fails to converge the following back-up options may be used:
 - i) A discriminant function [Brand, 1999] may be used in place of logistic.
 - ii) MCMC with adaptive rounding.

A sufficient number of imputations will be performed to ensure the stability of the estimates. The results of analysis from each complete imputed dataset will be combined using Rubin’s rule.

Table 3 Multiple Imputation Specifications) details the models, covariates and the seed to be used for the analyses.

Table 3 Multiple Imputation Specifications

Endpoint	Model	Covariates	Post-Baseline Timepoints Included in Prediction Model for Day X (X=2,...,29)	Initial Seed
Proportion of participants who have progression of COVID-19 at Day 29 (hospitalized >24h/death)	Monotone Binary Logistic Regression	Treatment, Age Group at Baseline, Sex	Day X-1	6862

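### The SAP calls the hypothetical estimand more conservative than treatment policy for non-inferiority; this is not generally true and can reverse when prohibited medication marks deterioration

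*SAP*

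**What the plan says.** SAP Section 1.1 handles three intercurrent events with a hypothetical strategy: treatment misallocation, discontinuation of study intervention, and use of medication listed as not permitted in Protocol Section 6.8.1 up to Day 29. The rationale is a single sentence: "A hypothetical estimand is used as this is considered more conservative than treatment policy and therefore more appropriate for a non-inferiority comparison".

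Section 4.2.2 gives the mechanics: "Data observed in the period following an intercurrent event (i.e. from the study day following the intercurrent event) will be excluded from the analysis". The excluded period is assumed missing at random. An event counts as intercurrent only if it comes before the primary endpoint.

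Section 6.2.8 replaces the excluded data day by day with a "logistic regression imputation model including the analysis model covariates and a parameter for COVID-19 progression status for the previous study day". Table 3 of the SAP lists the covariates as treatment, baseline age group and sex.

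Section 2.1 tests non-inferiority on the primary (hypothetical) estimand only, and that result gates the secondary endpoints. Section 4.2.3 plans a supplementary treatment-policy analysis in the ITT set. Section 4.2.4 plans a two-dimensional tipping-point analysis for both estimands.

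**The concern.** The primary endpoint is hospitalisation for more than 24 hours, or death. Suppose a participant worsens, is given a prohibited medication and is hospitalised two days later. The observed hospitalisation is dropped. The replacement is drawn as for any participant of that arm, age group and sex who had not progressed by the previous day. Nothing in the imputation model records that this participant was getting worse, so the missing-at-random assumption is weakest where the medication was started because of deterioration.

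If users have above-average risk, both arms lose events. The arm with more progression loses more of them, so the absolute risk difference shrinks, which makes a fixed 3.5-point margin easier to meet. Conservatism is the only reason given for making this the deciding analysis. If it fails, the chance of wrongly declaring 500 mg IM non-inferior can exceed the planned 2.5%.

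The SAP also handles prohibited medication by treatment policy in its equivalence analysis of viral-load AUC (Section 1.1). It does not explain why the preferred strategy differs between two claims of similarity.

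**Working it through.** **1. The plan's own figure.** SAP Section 5 plans 340 participants per arm for about 90% power, with a one-sided test at 2.5%. The event rates and margin behind this are given as: "assuming COVID-19 progression rates of 2% in the sotrovimab IM and IV arms and 3.5% non-inferiority margin on the risk difference scale".

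- Standard error = √(2 × 0.02 × 0.98 / 340) = 0.01074.
- Power = Φ(0.035 / 0.01074 − 1.96) = Φ(1.30) = 90.3%.
- The same method needs 337 per arm for 90%, against 340 planned.

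The sample size reproduces, and this point does not affect it.

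**2. Direction of the shift.** In each arm let u be the share with the intercurrent event, t their observed risk afterwards, and h the imputed risk. The hypothetical rate minus the treatment-policy rate is u(h − t). The IM − IV difference therefore moves by u_IM(h_IM − t_IM) − u_IV(h_IV − t_IV). The sign depends on whether users progress more or less often than imputed. No single direction follows from the method.

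**3. Medication marks deterioration.** The documents give neither u nor t, so these are assumptions. Take rates of 5.5% IM and 2.0% IV, a true difference equal to the margin. A share q of progressors in both arms takes prohibited medication first, half of users progress (t = 50%), and the medication itself does not change the outcome, so both estimands have the same true value.

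- u = q × p / t, where p is the arm's rate.
- Imputed risk h = (p − u × t) / (1 − u), specific to the arm. The hypothetical rate then equals h.
- False non-inferiority = Φ((0.035 − d) / SE − 1.96), where d is the resulting difference, at 340 per arm.

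| q | u, IM / IV | Rate, IM / IV | Difference (points) | False non-inferiority |
|---|---|---|---|---|
| 0 | 0 / 0 | 5.50% / 2.00% | 3.50 | 2.5% |
| 10% | 1.1% / 0.4% | 5.01% / 1.81% | 3.20 | 4.1% |
| 20% | 2.2% / 0.8% | 4.50% / 1.61% | 2.89 | 6.8% |
| 30% | 3.3% / 1.2% | 3.98% / 1.42% | 2.56 | 11.4% |

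For q = 20%, IM: (5.5 − 2.2 × 0.5) / 0.978 = 4.50%. IV: (2.0 − 0.8 × 0.5) / 0.992 = 1.61%.

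A 20,000-run simulation with multiple imputation and Rubin's rules gave 5.4%, 9.0% and 14.2% for q = 10%, 20% and 30%. Its baseline without any such events was 3.5%. It used a simplified arm-level imputation, not the SAP's daily model. Imputing from a pooled risk instead of an arm-specific one changes the difference by at most about 0.05 points, so the shrinkage comes from losing above-average-risk events.

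**4. Cases where the SAP's rationale holds.** Same underlying rates, so the hypothetical difference stays at 3.50 points and 2.5%.

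- Effective medication in average-risk users, taken by 20% in IM and 5% in IV. At 50% efficacy treatment policy gives 5.5 × 0.90 − 2.0 × 0.975 = 3.00 points (5.5% false non-inferiority). At 80% it gives 5.5 × 0.84 − 2.0 × 0.96 = 2.70 points (8.5%).
- Crossover misallocation of 5% in each arm: 5.325 − 2.175 = 3.15 points (4.3%). Of 10%: 5.15 − 2.35 = 2.80 points (7.0%).

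Each estimand is the safer one in some cases and the weaker one in others.

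**The case against.** The strongest reply is that the pathway is narrow. Only medication taken before the endpoint counts, data are dropped only from the following day, and earlier or same-day hospitalisations are kept. All participants receive standard of care (SAP Section 1.2). Protocol Section 6.8.1 exempts antivirals given as local standard of care, and exempts plasma or antibody given as standard of care to hospitalised participants. Few events may qualify. This stands, with one limit: the supplied protocol is Amendment 4, while the SAP follows Amendment 3, so the operative list cannot be seen.

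Second, a gap between two estimands is not in itself type I error. That is right. The inflation in the table is a failure of missing at random, and it arises because the assumed medication leaves the outcome unchanged and the imputation model carries no marker of worsening.

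Third, the treatment-policy and tipping-point analyses would reveal the problem. They would, but Section 2.1 gives neither a role in the decision, and the tipping-point results go to a heatmap with no threshold.

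A reader might go further and infer that the hypothetical estimand always pulls the arms together, or that both arms are imputed at one common risk. The documents support neither. The direction is conditional, as the fourth step shows, and treatment is in the imputation model.

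**Conclusion.** The blanket statement that the hypothetical estimand is more conservative is unsupported and is not generally true. It can be right for misallocation and for effective medication in average-risk users. It can be wrong for prohibited medication that marks deterioration. On the assumptions in the table (10–30% of progressors in both arms medicated first, half of users progressing, 340 per arm), a true 3.5-point difference shrinks to about 3.2–2.6 points and false non-inferiority rises from 2.5% to about 4–11%. These figures show what is possible; they do not estimate what happened. If few participants took qualifying medication before progressing, the effect is small.

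It is tempting to set this beside the reported 95% upper limit of 3.45% (Protocol Section 2.1), which is 0.05 points below the margin, and to infer that the choice of estimand decided the trial. The protocol does not say which estimand produced that limit and gives no count of discarded events, so the limit is not evidence on this point.

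**What to change.** - Remove the general conservatism claim. For each of the three intercurrent events, state the expected direction of the difference between the two strategies, and why.
- Conclude non-inferiority of 500 mg IM only if the 95% upper limit is below 3.5% under both the hypothetical and the planned treatment-policy estimands. Apply the same condition to the gate for the secondary endpoints.
- Report by arm the hospitalisations and deaths discarded after an intercurrent event.

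Requiring both guards against bias in either direction and needs no new data. In a simplified simulation at 340 per arm, with 10–20% of progressors medicated first and 30% of users progressing, false non-inferiority fell from about 5–8% under the hypothetical estimand alone to about 3%. Power under both was about 89% against the stated 90%, so the cost is about 1 point. Compared with the hypothetical analysis alone the loss would look larger, because discarding events raises that analysis's apparent power.

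The imputation model would still lack a marker of worsening, so the tipping-point analysis remains necessary. Because the Day 29 result is already reported, a joint rule adopted now should be labelled post hoc, with the two estimands shown side by side. The treatment-policy analysis uses the full ITT set, while the primary one excludes participants who failed key eligibility criteria, so that display should state both populations.
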